### Data Collection and Analysis Dataset:

Data will be collected on the AE, procedure and core lab echo CRFs. Data will be summarized on the Attempted Subjects analysis set.

### Analysis Method:

The proportion of subjects with device success will be presented with its associated 95% exact confidence interval at discharge, 30 days and at all later post-procedure intervals. The numerator will include subjects with success in all components of this endpoint. The denominator will include subjects who have success or at least one failure component present.

The proportion of subjects with success for each component of this endpoint will also be presented at discharge, 30 days and at all later post-procedure intervals; the numerator will include subjects with success, and the denominator will include subjects with non-missing data.

- MVARC defined procedural success

### Hypothesis/Decision Criteria:

No specific hypotheses or pass/fail criteria have been set. The analysis will be descriptive and no statistical hypothesis tests are planned.

### Endpoint Definition/Parameters to Be Estimated:

This endpoint is defined using variables on the AE, procedure, discharge, and core lab echo CRFs.

Procedural success is measured at 30 days. All of the following must be present:

- Device success (either optimal or acceptable, see definitions above); and
- Absence of major device or procedure related serious adverse events (AE, procedure, discharge CRFs), including:
  - Death

- Stroke
- Life-threatening bleeding (MVARC scale)
- Major vascular complication
- Major cardiac structural complications
- Stage 2 or 3 acute kidney injury (includes new dialysis)
- Myocardial infarction or coronary ischemia requiring percutaneous coronary intervention (PCI) or coronary artery bypass grafting (CABG)
- Severe hypotension, heart failure, or respiratory failure requiring intravenous pressors or invasive or mechanical heart failure treatment such as ultrafiltration or hemodynamic assist device, including intra-aortic balloon pumps or left ventricular or biventricular assist devices, or prolonged intubation for  $\geq$  48 hours.
- Any valve-related dysfunction, migration, thrombosis, or other complication requiring surgery or repeat intervention.

Device success has been defined above. By MVARC criteria, “optimal” device success requires a reduction in post-procedural MR to no more than trace levels, and “acceptable” device success is defined as a reduction in post-procedure MR by at least 1 class.

#### Data Collection and Analysis Dataset:

Data will be collected on the AE, procedure, discharge and core lab echo CRFs. Data will be summarized on the Attempted Subjects analysis set.

#### Analysis Method:

The proportion of subjects with device success will be presented with its associated 95% exact confidence interval at 30 days post-procedure. The numerator will include subjects with success in all components of this endpoint. The denominator will include subjects who have success or at least one failure component present.

The proportion of subjects with success for each component of this endpoint will also be presented; the numerator will include subjects with success, and the denominator will include subjects with non-missing data.

- MVARC defined individual subject success

## Hypothesis/Decision Criteria:

No specific hypotheses or pass/fail criteria have been set. The analysis will be descriptive and no statistical hypothesis tests are planned.

## Endpoint Definition/Parameters to Be Estimated:

This endpoint is defined using variables on the AE, procedure, discharge, baseline, follow-up, and core lab echo CRFs.

Individual subject success is measured at 1 year. All of the following must be present:

- Device success (either optimal or acceptable) (as defined above); and
- No re-hospitalizations or reinterventions for the underlying condition (e.g., MR heart failure) (AE CRF); and
- Improvement from baseline of symptoms (e.g., NYHA improvement  $\geq 1$  functional class) (baseline and follow-up CRFs); and
- Improvement from baseline in functional status (e.g., 6MWT improvement  $\geq 50$  meters) (baseline and follow-up CRFs); and
- Improvement from baseline in QoL (e.g., MLHFQ decline  $\geq 10$  points) (baseline and follow-up CRFs).

The following criterion in the MVARC definition is not included in the definition of individual subject success of this study due to data availability:

- Subject returned to pre-procedural settings

## Data Collection and Analysis Dataset:

Data will be collected on the AE, procedure, discharge, baseline, follow-up, and core lab echo CRFs. Data will be summarized on the Attempted Subjects analysis set.

## Analysis Method:

The proportion of subjects with device success will be presented with its associated 95% exact confidence interval at 1-year post-procedure. The numerator will include subjects with success in all components of this endpoint. The denominator will include subjects who have success or at least one failure component present.

The proportion of subjects with success for each component of this endpoint will also be presented; the numerator will include subjects with success, and the denominator will include subjects with non-missing data.

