## **Appendix B: Participant Information and Consent Form**

## **Appendix C: Instructions for Use**

## Appendix D: Endpoint Definitions

Analysis of study results will include the following additional MVARC defined exploratory endpoints:

**Technical Success** (measures at exit from catheterization laboratory)

All of the following must be present:

- I. Absence of procedural mortality; and
- II. Successful access, delivery, and retrieval of the device delivery system; and
- III. Successful deployment and correct positioning of the first intended device; and
- IV. Freedom from emergency surgery or reintervention related to the device or access procedure

**Device Success** (measured at 30 days and at all later post-procedural intervals):

All of the following must be present:

- I. Absence of procedural mortality or stroke; and
- II. Proper placement and positioning of the device; and
- III. Freedom from unplanned surgical or interventional procedures related to the device or access procedure; and
- IV. Continued intended safety and performance of the device, including:
  - a. No evidence of structural or functional failure
  - b. No specific device-related technical failure issues and complications
  - c. Reduction of MR to either optimal or acceptable levels without significant mitral stenosis (i.e., post-procedure EROA is 1.5 cm^2 with a transmural gradient <5 mm Hg), and with no greater than mild (1+) paravalvular MR (and without associated hemolysis)

**Procedural Success** (measured at 30 days)

All of the following must be present:

- I. Device success (either optimal or acceptable), and
- II. Absence of major device or procedure related serious adverse event, including:
  - a. Death
  - b. Stroke
  - c. Life-threatening bleeding (MVARC scale)
  - d. Major vascular complications
  - e. Major cardiac structural complications
  - f. Stage 2 or 3 acute kidney injury (includes new dialysis)
  - g. Myocardial infarction or coronary ischemia requiring PCI or CABG
  - h. Severe hypotension, heart failure, or respiratory failure requiring intravenous pressors or invasive or mechanical heart failure treatments such as ultrafiltration or hemodynamic assist devices, including intra-aortic balloon pumps or left ventricular or biventricular assist devices, or prolonged intubation for 48 h
  - i. Any valve-related dysfunction, migration, thrombosis, or other complication requiring surgery or repeat intervention

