## 1. Version History

Version	Summary of Changes	Author(s)/Title
1.0	

Not Applicable, New Document

	[name], Sr Prin Statistician
2.0	

Updated throughout to align with the current version of the CIP.

Added ISO 14155:2020 requirements per the current Statistical Analysis Plan Template B.

Section 7.8: Added description of the interim analyses performed.

Section 7.1.3: Added the analysis sets for consented subjects and approved subjects. Removed the per protocol and modified per protocol analysis datasets, since there were no previous analyses performed or future analyses planned for these populations.

Section 7.9.3: Added the MVARC criteria for technical, procedural, device and patient success per FDA request.

	[name], Senior Statistician
3.0	

Includes language to exclude echocardiography data after explant of the study valve from analysis.

Clarified greater severity between TTE and TEE will be reported where applicable.

Minor formatting updates and update to SAP template version C.

	[name], Senior Statistician
4.0	

Updated definition of LVOT Patency to align with current Mitral study definitions.

Included an additional contemporary definition for Mitral Valve Stenosis.

Updated French CIP protocol number and date, and formatted Australian CIP version date.

Added "Mild-Moderate" and "Moderate-Severe" as mitral regurgitation levels, and updated categorization.

Updated proportion confidence interval descriptions to exact confidence intervals

Added additional options for device relatedness to adverse event to align with current CEC charter.

	[name], Senior Statistician

Version	Summary of Changes	Author(s)/Title
	

• Refined MVARC composite endpoint denominators to denote inclusion of subjects with any failures.

• Replaced Approved with Attempted for the Analysis cohorts in various outcomes.

• Updated the method for Kaplan-Meier standard errors to be Greenwood throughout.

• Minor formatting updates.

	

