## 7.2 General Methodology

A comprehensive analysis of the pilot study results, as a whole, will be assessed to evaluate the overall risk/benefit balance for the patient population being treated. Pre-defined statistical “success” or “pass” criteria for the study endpoints are not applicable for this pilot study, as it is not a powered, hypothesis-driven study.

Each subject’s data will be reviewed individually and case summaries for all subjects will be provided to the FDA. In addition, descriptive statistics will be used to summarize the preoperative, operative, discharge, and follow-up clinical data. No statistical hypothesis tests are planned. The endpoint measures will be summarized by time point. Additionally, change from baseline will be presented for each outcome, as applicable.

To report the distributions of continuous variables, mean, standard deviation, minimum, median, first and third quartiles, and maximum will be presented. To report the distributions of categorical variables, counts and proportions will be provided. Proportions and associated 95% confidence intervals will be reported for endpoints, as applicable. For time to event data, Kaplan-Meier event rates will be presented at clinically meaningful post-operative time intervals, for instance, 30 days, 183 days, and annually thereafter (e.g., 365, 365×2, 365×3 days, etc.). At each time point with data, the product-limit estimate of the event rate, the number of subjects at risk, the number of subjects with events, the Greenwood standard error of the estimate, and the loglog transformed 95% confidence interval using the Greenwood standard error will be presented.

For subjects without an event, the date of censoring will be the latest date of all follow-up visits (including video contact, phone and/or mail correspondence), assessments, events (including death in those endpoints where death is not the endpoint) and study exits. For subjects whose exit reason is lost to follow-up, the last follow-up date will be the latest date of the follow-up visits (including video contact, phone and/or mail correspondence), assessments and events.

For analyses reporting the function of the study valve using echocardiographic or MDCT data, only data corresponding to the implanted study valve will be used; data post-explant or after reintervention in which the index study valve is no longer functioning will be excluded from the analysis.

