## **7.4 Handling of Missing, Unused, and Spurious Data and Dropouts**

Every effort will be undertaken to minimize missing, unused, and spurious data and dropouts. In time-to-event outcomes, drop-outs will be censored at the time of discontinuation, consistent with the Kaplan-Meier approach.

Unless otherwise specified in each objective, no statistical techniques will be used to impute missing data for continuous or categorical outcomes. If a subject's data are missing for any reason, that subject will not be included in that portion of the analysis. The number of subjects included in each analysis will be reported so that the reader can assess the potential impact of missing data.

In the case of partial dates, if only the month and year are known, the event or assessment will be analyzed as if it occurred on the 15th of that month. If only the year is known, the event or assessment will be analyzed as if it occurred on June 30th of that year. These resolutions of partial dates are subject to the restrictions that events must occur no earlier than the procedure date or after study exit. For more complex imputations of dates, determination will be made on a case-by-case basis based on the most suitable date range.

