### **7.9.3 Additional Exploratory Endpoints**

Event and endpoint definitions for this study's analysis will be based on those definitions outlined in the MVARC Consensus Document. Each subject's data will be reviewed individually and case summaries for all subjects will be provided. These endpoints are listed only in the CIP for the US and France.

- Measured by echo post-procedure through 5 years:
  - Reduction in MR Grade from baseline
  - No significant MV stenosis
  - LVOT patency
  - Improvement in LVEF
  - Improvement in cardiac output/cardiac index
  - Reduction in LV end-systolic and end-diastolic dimensions

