#### Endpoint Definition/Parameters to Be Estimated:

This endpoint is defined using variables on the AE, procedure and core lab echo CRFs.

Device success is measured at discharge, 30 days and at all later post-procedure intervals. All of the following must be present:

- Absence of procedural mortality or stroke (free from death and stroke within 30 days of procedure, AE CRF); and
- Proper placement and positioning of the device (TMVR implanted is "Yes", procedure CRF); and
- Freedom from unplanned surgical or interventional procedures related to the device or access procedure (Conversion to open MV replacement is "No" and Other repair surgery is "No", procedure CRF); and
- Continued intended safety and performance of the device, including
  - o No evidence of structural or functional failure (free from AEs for device malfunction for structural or functional failures, and free from explant and MV reinterventions, AE CRF)
    - Delivery failure (i.e., technical failure)
    - Structural failure
    - Functional failure
  - o No specific device-related technical failure issues and complications (core lab echo, AE, procedure CRF)
    - Paravalvular leak (core lab echo, AE CRF)
      - Major/Minor: Having a major paravalvular leak is considered as having a device failure.
    - Coronary vessel compression or obstruction (defined using CEC code, AE CRF)
      - Major/Minor: Having a major coronary vessel compression or obstruction is considered as having a device failure.
      - Symptomatic/Not symptomatic: Having a symptomatic coronary vessel compression or obstruction is considered as having a device failure.

- Requiring treatment/Not requiring treatment: Having a coronary vessel compression or obstruction requiring treatment is considered as having a device failure.
- Transient/Persistent: Having a persistent coronary vessel compression or obstruction is considered as having a device failure.
- Pericardial effusion (defined using CEC code, AE CRF)
  - Major/Minor: Having a major pericardial effusion is considered as having a device failure.
- Conversion to open mitral valve surgery during a transcatheter procedure (Conversion to open MV replacement is "No", procedure CRF)
- Device malpositioning (defined using CEC code, AE CRF)
- Device detachment (defined using CEC code, AE CRF)
  - Partial/Complete: Having a complete device detachment is considered as having a device failure.
- Device fracture (defined using CEC code, AE CRF)

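### Pilot SAP, exploratory 1-year individual subject success: a death after day 30 with no failed component leaves the denominator instead of counting as a failure

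*Combined protocol and SAP*

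**What the plan says.** All references are to the Pilot Study SAP unless stated otherwise.

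- **Section 7.9.3, individual subject success, endpoint definition:** "Individual subject success is measured at 1 year. All of the following must be present". The components are device success, no re-hospitalization or reintervention for the underlying condition, and improvement from baseline in NYHA class, 6MWT and MLHFQ. Death is not a component in its own right.
- **Section 7.9.3, device success, endpoint definition:** the mortality term is "free from death and stroke within 30 days of procedure". CIP-1403 Appendix D has the same limit: "Absence of procedural mortality or stroke; and".
- **Section 7.9.3, individual subject success, analysis method:** the numerator needs success in every component. For the denominator: "The denominator will include subjects who have success or at least one failure component present". Each component is also reported over its own non-missing data.
- **Section 7.4:** nothing is imputed unless an objective says so, and this one does not. When data are missing for any reason, "that subject will not be included in that portion of the analysis".
- **Section 1, version 4.0 entry:** "Refined MVARC composite endpoint denominators to denote inclusion of subjects with any failures". Death is not mentioned there.

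**The concern.** A subject who dies before the 1-year visit cannot have improved at 1 year and so cannot be an individual subject success. Under the stated rules, a death on day 20 is scored as a failure, while a death on day 200 may not be scored at all. The reported proportion then describes a group from which some of the worst outcomes have been removed, and it carries an exact confidence interval as if the denominator were clean. A reader of the 1-year rate could not tell how late deaths were classified.

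**Working it through.** The plan gives no rate, target or power for this endpoint, so there is no figure to reproduce. The check is a classification exercise followed by an illustration of size.

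**Step 1. Classification.** Score each component as success, failure or missing, then apply the denominator rule.

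| Subject | Event components | 1-year echo, NYHA, 6MWT, MLHFQ | Result |
|---|---|---|---|
| Dies by day 30 | mortality term failed | missing | failure, in denominator |
| Dies after day 30, earlier heart failure re-hospitalization | re-hospitalization term failed | missing | failure, in denominator |
| Dies after day 30, no failed component | all passed | missing | neither, dropped |

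Only the third row is affected.

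**Step 2. Size, with all survivors fully assessed.** Inputs:

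- N = 95, the worldwide cap in SAP section 6. Section 7.9.3 says of the exploratory endpoints, "These endpoints are listed only in the CIP for the US and France". The caps there are 70 and 20, so 90 and 70 are also shown.
- p = 40% success among everyone else. This is an assumption.
- d = deaths after day 30 with no failed component. This is an assumption.

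The rate as written is p. With those deaths counted as failures it is p(N − d)/N.

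| N | d | As written | Deaths as failures | Gap (points) |
|---|---|---|---|---|
| 95 | 3 | 40.0% | 36.8/95 = 38.7% | 1.3 |
| 95 | 5 | 40.0% | 36/95 = 37.9% | 2.1 |
| 95 | 10 | 40.0% | 34/95 = 35.8% | 4.2 |
| 90 | 5 | 40.0% | 34/90 = 37.8% | 2.2 |
| 70 | 5 | 40.0% | 26/70 = 37.1% | 2.9 |

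If only 5 of 10 late deaths lack a failed component, the rate as written is 34/(95 − 5) = 37.8% against 34/95 = 35.8%, a gap of 2.0 points.

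For scale, the only mortality figure in the SAP is 5% per year without surgery (section 3). Over days 31 to 365 that gives 95 × (1 − 0.95^(335/365)) ≈ 4.4 deaths. It is not a rate after implantation, and it does not say how many deaths would lack a failed component. The exact 95% interval for 36/90 is 29.8% to 50.9%.

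**Step 3. Survivors with incomplete 1-year data.** The same sentence keeps such a survivor only if a failure was observed. Let a share r of survivors be incomplete, let q be their true success rate, and let f be the share of their failures that is observed. As shares of survivors:

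- observed successes: s = p(1 − r)
- observed failures: o = (1 − p)(1 − r) + (1 − q)·r·f
- rate as written: s/(s + o)
- true rate among survivors: p(1 − r) + q·r

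Take N = 95, d = 5 (90 survivors), p = 40% and r = 20%.

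| | q = 40%, f = 80% | q = 10%, f = 50% |
|---|---|---|
| As written | 0.32/0.896 = 35.71% | 0.32/0.89 = 35.96% |
| True, survivors only | 40.00% | 34.00% |
| Survivor effect | −4.3 points | +2.0 points |
| True, deaths as failures | 36/95 = 37.89% | 30.6/95 = 32.21% |
| Net error as written | −2.2 points | +3.7 points |
| Deaths as failures, nothing else changed | 28.8/85.64 = 33.63% (−4.3) | 28.8/85.1 = 33.84% (+1.6) |
| Bounds: s × 90/95 to (1 − o) × 90/95 | 30.3% to 40.2% | 30.3% to 40.7% |

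The survivor effect changes sign with q and f, and the documents give neither. The bounds contain the true rate in both columns.

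**The case against.** **The list of conditions could already fail the dead.** Requiring every component to be present might be read as making an absent improvement a failure. No section says so. That reading would also turn every dropout into a failure, against section 7.4, and would leave the denominator sentence with nothing to do.

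**Deaths are reported elsewhere.** This is largely true. Section 7.1.1 gives disposition with deaths and visit completion, section 7.4 the number in each analysis, the NYHA analysis a count of deaths before each visit, and section 7.10 a death listing. Section 7.2 adds that "case summaries for all subjects will be provided to the FDA". These show that deaths occurred and supply part of the counts requested below. None says whether a given death was a failure or was dropped from this composite.

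**It is a design choice.** The denominators were deliberately refined in version 4.0, and Appendix D of the CIP names only procedural mortality. It stands that scoring later deaths as failures adds a rule the CIP does not state. It does not follow that the present rule gives a sensible 1-year success rate, since it removes subjects who cannot be successes.

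**The numbers are assumed and small.** This stands in full.

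**Conclusion.** The point holds, as a minor one. As written, the rule drops a late death with no failed component from the 1-year individual subject success rate. If survivors are fully assessed and at least one success is observed, each such death raises the rate. At an assumed 40% success, the overstatement is 1.3 to 4.2 points for 3 to 10 such deaths of 95, well inside the width of the exact interval.

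A reader might infer more, in four ways that the documents do not support:

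- **That all late deaths vanish.** Those with a heart failure re-hospitalization, reintervention, explant or major device complication stay in as failures.
- **That the reported rate is too high overall, or that incomplete survivors pull it down by a predictable amount.** Their effect can go either way, because their success rate is unknown. For the same reason it cannot be said in general that scoring deaths as failures, with nothing else changed, makes the estimate worse: in step 3 it does so in one case and helps in the other.
- **That the main conclusions are at risk.** The endpoint is exploratory and descriptive, with no pass criterion, and no primary or secondary endpoint uses this denominator.
- **That the transseptal early feasibility study is affected.** The sentence stands in the Pilot Study SAP, which is written for CIP-1403.

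**What to change.** In SAP section 7.9.3, individual subject success (endpoint definition and analysis method):

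1. Count death from any cause before the 1-year assessment as failure of individual subject success.
2. Beside the rate, state the numbers attempted, dead, and alive but not fully evaluable.
3. For survivors who are not fully evaluable and have no observed failure, give the rate with all of them counted as successes and with all counted as failures.
4. Editorial: the analysis methods for procedural success and for individual subject success both call the reported proportion device success. Name the endpoint concerned in each.

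The cost is SAP wording and reprogramming from data already collected. SAP section 7.12 calls for a protocol revision if the change precedes the analysis, or a reasoned entry in the clinical study report if it follows. The drawbacks are that the rate may be slightly less favourable, is shown with a range, may differ from any 1-year rate already reported, and rests on a rule that CIP-1403 Appendix D does not contain.
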